#### **4.6 Quality of Life**

The quality of life questionnaires include disease specific (AVVQ) and generic (EQ5D & SF-36) components. AVVQ will be recoded according to its manual. The SF-36 will be scored using Health Outcome Scoring Software 4.0 for the physical health and mental health dimensions, and all eight scales, including physical functioning, role limitations due to physical health, role limitations due to emotional problems, energy/fatigue, emotional well-being, social functioning, pain, and general health. The index-based values ('utilities') will be calculated by the EQ-5D-5L Crosswalk Index Value Calculator downloaded from the EQ-5D official website.

The QoL scores will be presented using line plots for each study arm to illustrate trends in AVVQ score, SF-36 and EQ-5D-5L over time (Figures 8-10). Depending on the distribution of the data, the means and 95% CI of means or medians and inter-quartile ranges at baseline, 6-weeks, 6-months and 12-months after randomisation, will be reported (Table 9). Analysis of variance will be used to explore changes in QoL over time and assess the difference between the two intervention groups.

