4.3.2 Secondary outcome measures

A number of secondary outcome measures will be evaluated in the EVRA study:

1. Ulcer Healing Rate: Healing rate will be reported at 24 weeks in addition to time to ulcer healing to allow comparison with other published studies.
2. Ulcer recurrence / Ulcer Free Time: Will be calculated up to 1 year for each study arm and with the extension, up to 5 years (median approximately 3.7 years). This will allow a very practical and easily understood assessment of the clinical difference between the 2 arms of the study. This will also allow comparison with other studies that have reported this outcome. In order to facilitate accurate calculation of reoccurrence / ulcer free time, clinical follow up will be continued after ulcer healing up to 1 year after randomisation.
3. Quality Of Life (QoL): Disease specific (AVVQ) and generic (EQ5D & SF36) quality of life assessments will be compared at 6 weeks post randomisation, 6 months, 12 months and at one time point between October 2018 and March 2019. The 6-week questionnaire will be given to the patient at the follow-up appointment, whereas other QoL questionnaires will be sent to the patient or completed by the patient via telephone. AVVQ is the most widely utilised disease specific QoL tool in venous disease and has been extensively validated. A score out of 100 points is calculated, with a higher score indicating more severe QoL impairment. Changes in QoL scores will offer a comparison with other studies and, in the standard treatment arm, will allow an assessment of the natural history of venous ulceration treated with compression.

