6.3 BASELINE VISIT

Patients will undergo detailed clinical assessment by the research nurse as part of the baseline evaluation (see *Appendix 1*). Recorded assessments will include:

- Demographic details (age, sex, ethnicity)
- Pregnancy test for woman of child bearing potential
- General clinical details (body mass index, ankle brachial pressure index – performed within previous 4 weeks, comorbidities, medication history)
- Ulcer details (duration, progression, previous ulcer history, size of current ulcer – using photography and planimetry)
- Details of venous disease (previous deep vein thrombosis, previous venous interventions, pattern of venous reflux on duplex)

Additional assessments will include:

- Assessment of Clinical, Etiologic, Anatomic, Pathophysiological (CEAP) score
- Assessment of venous clinical severity score (VCSS)
- Disease specific (Aberdeen varicose vein questionnaire – AVVQ) and generic (EuroQoL 5D – EQ5D & short form (SF) 36) quality of life assessments

At this visit, eligible and consenting patients will be randomised into the trial.

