#### ***Secondary Outcomes***

- Ulcer Healing Rate: 24-week healing rate will be reported in addition to time to ulcer healing.
- Ulcer reoccurrence / Ulcer Free Time: Will be calculated up to 1 year for each study arm.
- Quality Of Life (QoL): Disease specific (AVVQ) and generic (EQ5D & SF36) quality of life assessments will be compared at 6 weeks post randomisation, 6 months and 12 months.
- Health Economic Assessment
- Other Markers of Clinical Success: The Venous Clinical Severity Score (VCSS) and will be assessed at 6 weeks. In addition, the incidence of complications related to the endovenous intervention as well as the presence of residual / recurrent varicose veins will also be assessed at 6 weeks.

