## 1.6 Randomisation

The normal clinical team will make initial contact with potentially eligible patients at the referral visit.

Those who consent will be registered on the InForm ITM (Integrated Trial Management) System, a web-based data entry system, which is maintained by ICTU, and their eligibility for the study confirmed. A randomization list will be loaded onto the InForm system for each centre (as stratification will be by centre) before recruitment commences, having been prepared

in advance by a statistician who is independent of the study. Each potential participant, if confirmed to be eligible, will be assigned the next available entry in the appropriate randomization list (i.e. without foreknowledge). Thereafter, treatment allocation will not be blinded (with the exception of assessment of ulcer healing). For patients with bilateral venous ulceration, the worst leg (according to the patient) will be designated the ‘reference leg’. Interventions may be performed on both legs, if deemed appropriate by the responsible clinician.

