### **4.4 Primary Endpoints**

The primary outcome is time to complete healing and we will test the hypothesis that there is no difference in this between the control and intervention groups using a Cox model with study centre as a random effect (Table 6). Kaplan-Meier survival curves and the log-ran test will also be presented (Figure 3). As a subsidiary analysis we will investigate the effect of potential confounders listed in section 2.1 (age, ulcer chronicity and ulcer size) on the treatment effect and on time to complete healing using Cox regression, again with centre included in the Cox regression analysis as random effect (Table 6). To assess whether the treatment effect is consistent across all patient sub-groups, the hazard ratios and 95% confidence intervals for treatment from the above Cox regression models (with adjustment for potential confounders and centre as a random effect) will be re-calculated for each of the following subgroups separately; BMI (<23, 23.0-25.0, 25.01-30.0, > 30), Age ( $\leq 49$ , 50-69, 70+), gender (male, female), smoking (Never, previous, current), ulcer size (by quartile), ulcer duration (by quartile), history of deep vein thrombosis (yes, no), history of rheumatoid arthritis (yes, no), taking anti-platelet therapy (yes, no), history of intervention on previous leg ulcer (yes, no intervention, no previous ulcer) and baseline EQ5D (by quartile). The results will be presented using a Forest plot (Figure 4), with the overall result also included at the bottom. We will also use Cox regression to look for differences between the treatment arms by type of endovenous treatment (Endothermal alone, Foam sclerotherapy alone, Mechanochemical alone (MOCA), Endothermal plus Foam, or MOCA plus Foam). Results (hazard ratios and 95% confidence intervals will also be presented graphically in the Forest plot (Figure 5). These subsidiary analyses are intended to provide reassurance that the observed treatment effect is consistent across all patient sub-groups. The study is not powered to detect differences between sub-groups and any observed patterns should be interpreted extremely cautiously, owing to the smaller numbers and increased chance of Type I error. For Cox regression models the proportionality assumption will be assessed graphically (using diagnostic plots) and using Grambsch and Therneau tests and overall fit will be assessed graphically by plotting the Nelson-Aalen cumulative hazard function versus the Cox-Snell residuals and comparing to a 45°reference line.

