
#### 4.5 Ulcer Free Time to 1 year and 24-week Ulcer Healing Rate

Table 7 summarises the ulcer free time to 1 year and 24-week ulcer healing rate between the two arms. In the case that a patient is dead, withdrawn or lost to follow-up before 1 year, ulcer free time will be calculated as the time from randomisation until last follow-up. Multiple linear regression will be used to assess the difference between the treatments arms, with centre as a random effect, before and after adjustment for age, ulcer size and ulcer chronicity (Table 8). Graphical methods will be used to assess whether the assumption of normality is met. If the assumption of normality is not met, and there is no suitable transformation, ulcer free time will be categorized (by quartiles) and the analysis will instead be performed using ordinal regression. Model fit will be assessed using residual plots and/or goodness-of-fit tests, as appropriate. The 24-week healing rate and associated 95% confidence interval will be obtained from the Kaplan-Meier analysis (4.3). The primary analysis will be based on study participants with at least 1 year of follow up only (as explained in 2.2). As a sensitivity analysis we will repeat the above regression model (adjusted for age, ulcer size and ulcer chronicity, and centre) using all the study participants, irrespective of length of follow up.

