#### **4.7 Markers for Clinical Success**

Clinical success will be assessed using the Venous Clinical Severity Score (VCSS), which is measured at baseline and 6 weeks post-randomisation. The change in clinical classification in the Clinical, Etiologic, Anatomic, Pathophysiologic (CEAP) score at 6 weeks post-randomization from baseline will be reported and the chi-square test will be used to compare between the two arms. Similarly, change in VCSS score will be compared between the two arms using the t-test (assuming change in VCSS is normally distributed) or appropriate non-parametric test (if change in VCSS is not normally distributed).

Table 10 shows the proportions of patients with downgrade of clinical classification from C6 to C5 at 6-weeks post-randomisation and VCSS score. The VCSS scores at 6 weeks post-randomization and baseline will be summarised using boxplot for both arms (Figure 11).

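### SAP 4.6 and 4.7 compare QoL and VCSS between arms with no stated baseline covariate or centre term, giving up precision that the collected data could provide

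*SAP*

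**What the plan says.** SAP 4.6 (Quality of Life) states: "Analysis of variance will be used to explore changes in QoL over time and assess the difference between the two intervention groups". SAP 4.7 states that "change in VCSS score will be compared between the two arms using the t-test", with a non-parametric test if change is not normally distributed. Neither section mentions baseline score as a covariate or centre. Nothing elsewhere supplies them: SAP 2.1 says only how QoL will be summarised, and Protocol 7.2 places centre in the Cox regression only.

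These are formal comparisons. SAP 1.4 lists QoL as a secondary outcome for which "quality of life assessments will be compared at 6 weeks post randomisation, 6 months and 12 months", and SAP 2.5 applies a two-sided 5% test to secondary outcomes.

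The missing terms are available:

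- Protocol 6.3 collects AVVQ, EQ-5D and SF-36 at baseline, together with "Assessment of venous clinical severity score (VCSS").
- On centre, SAP 1.6 says "A randomization list will be loaded onto the InForm system for each centre (as stratification will be by centre) before recruitment commences".
- SAP 4.4 tests the primary outcome "using a Cox model with study centre as a random effect (Table 6").
- SAP 4.5 says of ulcer-free time: "Multiple linear regression will be used to assess the difference between the treatments arms, with centre as a random effect". That model is also fitted with age, ulcer size and ulcer chronicity.

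**The concern.** A change score forces the slope on baseline to be 1, and a follow-up-only comparison forces it to be 0. ANCOVA estimates the slope, so in large samples its variance is never greater than either. When randomisation is stratified by centre and the analysis ignores centre, between-centre variation stays in the residual and the reported standard error is too large. The QoL and VCSS comparisons may therefore give wider intervals than the same data allow. The SAP gives no reason for treating these outcomes differently from healing and ulcer-free time.

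SAP 4.6 is also loosely worded. It speaks of change over time, and Protocol 4.3.2 says "Changes in QoL scores will offer a comparison with other studies", so a change comparison is the main reading. The visit list in SAP 1.4, taken alone, would also fit a follow-up-only comparison, so both are worked through.

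**Working it through.** **The plan's own figures.** Neither document gives a sample size, power or precision figure for QoL or VCSS. The only calculation is for healing (Protocol 7.1). Its hazard ratio is ln(0.25)/ln(0.40) = 1.513. Freedman's formula at two-sided 5% and 90% power gives 253 events; 253/0.675 = 375 patients, and 375/0.90 is about 416. The protocol states 254 and 416. That calculation reproduces and is not touched by this point.

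**Assumed inputs.** r is the correlation between baseline and follow-up score. k is the baseline SD divided by the follow-up SD. ICC is the centre intraclass correlation of the analysed score. None is in the documents. A k below 1 is plausible for VCSS, because Protocol 3.2 requires a current ulcer and so restricts the spread at entry.

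**Baseline covariate.** In units of the follow-up variance:

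- change score: 1 + k² − 2rk
- follow-up only: 1
- ANCOVA: 1 − r²

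The change-score variance exceeds the ANCOVA variance by (k − r)², so the loss is zero when r = k. At k = 1 and r = 0.3, for example, the ratio is (1 + 1 − 0.6)/(1 − 0.09) = 1.40/0.91 = 1.538, and √1.538 = 1.240, a CI 24.0% wider.

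| Stated analysis versus ANCOVA | r = 0.3 | r = 0.5 | r = 0.7 |
|---|---|---|---|
| Change, k = 1: variance ratio | 1.538 | 1.333 | 1.176 |
| Change, k = 1: CI wider by | 24.0% | 15.5% | 8.5% |
| Change, k = 0.7: variance ratio | 1.176 | 1.053 | 1.000 |
| Change, k = 0.7: CI wider by | 8.4% | 2.6% | 0.0% |
| Change, k = 0.5: variance ratio | 1.044 | 1.000 | 1.078 |
| Change, k = 0.5: CI wider by | 2.2% | 0.0% | 3.8% |
| Follow-up only: CI wider by | 4.8% | 15.5% | 40.0% |

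At r = 0.5 and k = 1, the ratio of 1.333 means that adjustment is worth about 33% more patients.

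**Centre term.** Assume the arms are balanced within centre. Leaving centre out multiplies the variance estimate by 1/(1 − ICC). The true two-sided type I error becomes 2 × (1 − Φ(1.96/√(1 − ICC))).

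| ICC | Variance factor | CI wider by | Type I error |
|---|---|---|---|
| 0.01 | 1.010 | 0.5% | 4.9% |
| 0.05 | 1.053 | 2.6% | 4.4% |
| 0.10 | 1.111 | 5.4% | 3.9% |

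**Both omissions**, with a change score and ICC 0.05: multiply the variance ratios by 1.053 and take the square root. At r = 0.3, 0.5 and 0.7, the CI is 27.3%, 18.5% and 11.3% wider for k = 1, and 11.3%, 5.3% and 2.6% wider for k = 0.7.

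**Simulation check.** This assumed 380 patients in 19 equal centres, with 2,000 runs per setting, and compared a t-test on change with ANCOVA including centre. Over the same r values at ICC 0.05, the standard-error ratios were 1.269, 1.181 and 1.110 for k = 1, and 1.109, 1.050 and 1.024 for k = 0.7. These agree with the formulas.

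All these are ratios, so they do not depend on the QoL sample size. That size will be below the number randomised in any case, because Protocol 3.2 restricts patients who cannot speak or understand English to healing data.

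**The case against.** The strongest reply is that nothing here is wrong. A t-test on change is a conventional, valid comparison in a randomised trial, and Protocol 4.3.2 gives a reason to work with changes. Every input to the size is assumed, and the grid contains zeros. VCSS, where the unadjusted change test is explicit, is also where k below 1 is most plausible and the gain smallest. All of this stands, and it limits the point to efficiency.

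The case against the centre term also has force. Stable centre differences cancel in a change score, so only the ICC of the change itself matters. The documents describe lists by centre but do not mention blocking, so balance within centre is an assumption. In a second simulation (20 centres of 19 patients, randomised within centre), the true sampling SD was essentially unchanged by the centre term. Its benefit is a standard error that reflects the design and consistency with SAP 4.4 and 4.5; most of any gain comes from baseline.

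Two further arguments are weaker. First, the SAP 4.6 analysis could be a repeated-measures ANOVA with baseline as a time point. Its arm-by-time contrast at each visit is then a change contrast, so the change-score figures apply. Second, QoL could be seen as descriptive, since the shell for SAP Table 9 has no column for a treatment difference. But SAP 4.6 says that the arms will be compared, and SAP 2.5 says that secondary outcomes will be tested.

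Adjustment does need a rule for a missing baseline score, a covariance structure and an adjusted counterpart to the non-parametric VCSS test. These are routine.

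**Conclusion.** The concern holds as a point of efficiency on named secondary outcomes, and the change should be made. Under randomisation with complete data the stated comparisons are unbiased, and leaving out centre is slightly conservative.

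The loss cannot be fixed from the documents. On the change-score reading, with r from 0.3 to 0.7, omitting baseline widens the 95% CI by about 8% to 24% if the SDs are equal, and by 0% to 8% if the baseline SD is 0.5 to 0.7 of the follow-up SD. If the QoL analysis is follow-up only, the range is 5% to 40%. Centre adds 0.5% to 5.4% for an ICC of 0.01 to 0.10 with arms balanced within centre. The primary endpoint and sample size do not change.

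**What to change.** **SAP 4.6.** For each QoL score, specify a linear mixed model of the 6-week, 6-month and 12-month values. Include fixed effects for treatment, visit, treatment-by-visit and baseline score, and centre as a random effect. State the within-patient covariance structure. Use all available visits, and report the arm difference with 95% CI at each visit, with a place for it in Table 9.

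**SAP 4.7.** Specify ANCOVA of 6-week VCSS on arm, baseline VCSS and centre, with a bootstrap or non-parametric check if residuals are skewed.

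**Both sections.** State how a missing baseline score is handled, so that adjustment does not drop patients who have follow-up scores. Change-from-baseline summaries can stay as description, for the comparison with other studies that Protocol 4.3.2 intends.

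The cost is a few sentences of SAP wording and routine programming. No new data, visits or design change are needed.

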6.4.2 Further follow-up

- Assessments of disease specific and generic quality of life (AVVQ, EQ5D & SF36) by means of self-completed questionnaire at 6 months and 12 months post-randomization (sent to the patient).
- The research team will perform monthly telephone evaluation of the patient and access the community notes or telephone the community nurses in order to collect and verify the data collected.
- Once the research team has been informed that the ulcer has healed the patient will undergo an urgent verification visit

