7.3 MISSING, UNUSED AND SPURIOUS DATA

There will be no data imputation for missing data in the primary endpoint (time to healing) and the secondary endpoint of ulcer free time. Any imputation methods used may be proposed for purposes of sensitivity analysis for other secondary outcomes, including ulcer healing rate, QoL and markers of clinical success. Imputation methods will be fully documented in the SAP.

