## 2. General Considerations

### 2.1 Analysis Strategy

All the primary analyses will be on an intention-to-treat basis. Histograms and boxplots will be used to check the distribution and possible outliers for continuous variables. Mathematical transformations will be applied, where appropriate, in order to render the continuous variables

distribution normally distributed. Continuous variables that follow an approximately normal distribution will be summarised using means and standard deviations. Skewed continuous variables will be summarised using medians and inter-quartile ranges. Categorical variables will be summarised using frequencies and percentages.

The primary outcome is time to complete healing and we will test the hypothesis that there is no difference in this between the control and intervention groups using a Cox model with study centre as a random effect. Kaplan-Meier survival curves will also be presented. As a subsidiary analysis we will investigate the effect of potential confounders (age, ulcer chronicity and ulcer size) on the treatment effect and time to complete healing using Cox regression, again with centre included in the Cox regression analysis as random effect (Table 9).

For the secondary outcome of ulcer free time, multiple regression (ordinal, if not normally distributed) will be used to adjust for the above covariates.

The quality of life (QoL) data will be summarised across baseline, 6-week, 6-month and 12-month after randomisation for both arms by means and 95% confidence intervals (CI) or median and inter quartiles, depending on the distribution of the data.

Health economic assessment will be carried by the trial health economist and thus will not be included in this statistical analysis plan.

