### **2.4 Missing Data**

There will be no data imputation for missing data in the primary endpoint (time to healing) and the secondary endpoints of 24-week healing rate and ulcer free time. However, the level and pattern of the missing data in the baseline variables and outcomes will be reported. The potential causes of any missingness will be investigated and documented as far as possible. Any missing data will be dealt with using methods appropriate to the conjectured missingness mechanism and level of missingness.

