Pathophysiologic dysfunction		
Reflux		
Obstruction		
Both		
No venous cause		
VCSS Score		
Palpable pedal pulses		
Yes		
No		

\* Data presented as frequency (percentage) for categorical variables and median (range) for continuous variables

†A patient can have both deep vein reflux and obstruction

Table 5 Treatment summary

	EVRA N=	Standard N=
Endothermal only		
Foam only		
Mechanochemical ablation (MOCA) only		
Endothermal and Foam		
MOCA and Foam		

\* *Data presented as frequency (percentage)*

Table 6 Time to ulcer healing in patients with chronic venous ulceration (Cox regression model)

	Univariate model*		Multivariate model†	
	HR (95% CI)	P value	HR (95% CI)	P value
Treatment				
Standard arm				
EVRA				
Age (yrs)				
Ulcer chronicity (mths)				
Ulcer size				
1 st Quartile				
2 nd Quartile				
3 rd Quartile				
4 th Quartile				

\* Adjusted by centre (centre included in the model as a random effect)

† Adjusted by centre, age, ulcer size and chronicity (centre included in the model as random effect and age, ulcer size and chronicity as fixed effects).

Table 7 Summary of 12-week and 24-week ulcer healing rate and ulcer free time\*

	EVRA N=	Standard N=
12-week ulcer healing rate		
24-week ulcer healing rate		
No. of patients with recurrent ulcer		
Ulcer free time		

\* Data presented as frequency (percentage) for categorical variables and median (range) for continuous variables

Table 8 Multiple linear regression (ordinal regression) for ulcer free time (days) to 1 year in patients with chronic venous ulceration

	Univariate model*		Multivariate model†	
	Coefficient (95% CI)	P value	Coefficient (95% CI)	P value
Treatment				
Standard arm				
EVRA				
Age (yrs)				
Ulcer chronicity (mths)				
Ulcer size				
1 st Quartile				
2 nd Quartile				
3 rd Quartile				
4 th Quartile				

\* Adjusted by centre (centre included in the model as a random effect)

† Adjusted by centre, age, ulcer size and chronicity (centre included in the model as random effect and age, ulcer size and chronicity as fixed effects).

Table 9 Summary of quality of life (AVVQ, EQ-5D, SF36) at baseline, 6 weeks, 6 months and 12 months after randomisation

	N	EVRA	Standard
		Mean (SD)	Mean (SD)
AVVQ			
Baseline			
6 weeks			
6 months			
12 months			

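### The quality-of-life test is an unspecified analysis of variance: its usual across-visit forms ignore within-patient correlation or use complete cases only, and no between-arm estimate is specified at each visit.

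*SAP*

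**What the plan says.** SAP 1.4 defines the outcome visit by visit: disease-specific and generic "quality of life assessments will be compared at 6 weeks post randomisation, 6 months and 12 months". Protocol 4.3.2 names the same three visits and adds one extension time point, which Protocol 7.2 leaves to a separate SAP.

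The only test is in SAP 4.6: "Analysis of variance will be used to explore changes in QoL over time and assess the difference between the two intervention groups". SAP 2.5 applies a two-sided 5% level to secondary outcomes, without multiplicity adjustment.

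The remaining quality-of-life text is descriptive. SAP 2.1 says the data will be "summarised across baseline, 6-week, 6-month and 12-month after randomisation for both arms". Table 9, titled "Summary of quality of life (AVVQ, EQ-5D, SF36) at baseline, 6 weeks, 6 months and 12 months after randomisation", has columns for N and for mean (SD) in each arm, but none for a difference, a confidence interval or a P value. Tables 6 and 8 do have effect, interval and P value columns for time to healing and ulcer free time.

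On missing forms, SAP 2.4 rules out imputation for the two healing endpoints and ulcer free time. Otherwise it says: "Any missing data will be dealt with using methods appropriate to the conjectured missingness mechanism and level of missingness". Protocol 7.3 says imputation methods "may be proposed for purposes of sensitivity analysis for other secondary outcomes, including ulcer healing rate, QoL and markers of clinical success" and defers the detail to the SAP, which names no method.

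**The concern.** Each patient is due four forms in the first year: baseline, 6 weeks, 6 months and 12 months. A method that covers change over time has to deal with three things, and the sentence in SAP 4.6 settles none of them.

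- **Correlation.** Forms from one patient are not independent. The SAP names a random effect for centre in its healing and ulcer-free-time models, but no patient effect for quality of life.
- **Missing forms.** These are foreseeable. Protocol 4.4 expects some patients to stop the questionnaires while still giving healing data, and the 6- and 12-month forms are completed away from clinic. For ulcer free time, SAP 2.2 states a complete-case rule and admits the possible bias. For quality of life there is no rule.
- **The quantity estimated.** The outcome is a comparison at each visit, whereas an arm main effect averages over visits. Protocol 5.4 allows standard-arm patients ablation after confirmed healing or at 6 months, so the arm difference may well change between visits.

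At stake are the validity and precision of the quality-of-life intervals and P values. The choice among readings could also be made after the data are seen.

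**Working it through.** **Inputs from the documents.** Four forms per patient to one year, three of them after baseline (SAP 2.1, 4.6); target of 450 patients, 1:1 (Protocol 7.1, 4); two-sided 5% (SAP 2.5). The documents give no SD, effect size, correlation or return rate for quality of life, so there is no plan figure to reproduce here.

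**Assumptions, not in the documents.** Within-patient correlation ρ of 0.3 to 0.7, equal between all visits; 5% to 20% of forms missing per visit.

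**1. Forms treated as independent rows.** With m forms per patient, the true variance of the arm main effect is 1 + (m − 1)ρ times the variance assumed. The true type I error of the 5% test is 2Φ(−1.96/√[1 + (m − 1)ρ]). For m = 4 and ρ = 0.5, the factor is 2.5, its root is 1.58, 1.96/1.58 = 1.24, and the error is 21.5%. A simulation of a two-way arm-by-visit analysis (225 per arm, 4,000 runs per setting) is shown in brackets.

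| ρ | 3 post-baseline forms | 4 forms |
|---|---|---|
| 0.3 | factor 1.6: 12.1% (12.7%) | factor 1.9: 15.5% (16.2%) |
| 0.5 | factor 2.0: 16.6% (16.8%) | factor 2.5: 21.5% (21.7%) |
| 0.7 | factor 2.4: 20.6% (20.4%) | factor 3.1: 26.6% (26.8%) |

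The arm-by-visit test errs the other way: its simulated type I error was 1.7% or less throughout.

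**2. Complete cases only.** If a share q is missing independently at each of four visits, (1 − q)⁴ of patients have every form.

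| q | share complete | of 450 | forms available at each visit |
|---|---|---|---|
| 5% | 82% | 367 | 428 |
| 10% | 66% | 295 | 405 |
| 15% | 52% | 235 | 382 |
| 20% | 41% | 184 | 360 |

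This depends on the missingness pattern. If every baseline form is present, the share is (1 − q)³, from 86% to 51%. If returns fell to an assumed 95%, 85% and 80% over the three later visits, independence gives 0.95 × 0.85 × 0.80 = 65% complete. Monotone dropout gives 80%. Against using all available forms, the 6-week standard error is then √(0.95/0.646) = 1.21 times as large under independence and √(0.95/0.80) = 1.09 times under monotone dropout. At 12 months the ratios are √(0.80/0.646) = 1.11 and 1.00.

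**3. What a main effect estimates.** Take illustrative true differences of 0.4, 0.2 and 0 SD at the three visits. Their average is 0.2 SD, which describes only the middle visit. With baseline as a fourth level, the average is (0 + 0.4 + 0.2 + 0)/4 = 0.15 SD. A constant effect shrinks to 3/4 in the same way.

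**4. Value of baseline adjustment.** Leaving the baseline score out of a visit-specific comparison makes its standard error 1/√(1 − ρ²) times as large: 1.05 at ρ = 0.3, 1.15 at 0.5 and 1.40 at 0.7.

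**The case against.** The strongest defence is that SAP 4.6 does not commit to a bad analysis. Since the outcome is to be compared at each visit, a separate analysis of variance per visit is a natural reading. It uses one value per patient, needs no complete set of forms and gives per-visit comparisons. A repeated-measures analysis with arm-by-visit contrasts could give them too. SAP 2.4 leaves room for a missing-data method, Protocol 7.3 allows imputation for quality of life as a sensitivity analysis, and the sentence speaks of exploring.

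Much of this stands, and it rules out several stronger conclusions that a reader might draw:

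- That the SAP will pool repeated forms as independent, or will delete patients with a missing form. Neither is stated; each is the consequence of one usual form of the method.
- That analysis of variance cannot yield per-visit differences. It can; the gap is that none is specified.
- That inference would be uniformly too optimistic. With forms treated as independent, the interaction test is conservative.
- That the later forms come by post only, so returns must be poor. Protocol 4.3.2 also allows telephone completion.

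What the defence does not supply is a specification. Separate analyses per visit would not model change over time, which the same sentence sets as an aim. The missing-data text names no method. The sentence also covers assessing the difference between arms, and secondary outcomes are tested at 5%.

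**Conclusion.** The point holds as a specification defect in a secondary analysis. The single inferential sentence admits readings whose type I error for the arm effect ranges from nominal to 12-21% (three forms) or 16-27% (four forms), and readings that use anything from every returned form to complete cases alone. Complete cases would be about 82% to 41% of patients under independent missingness of 5-20% per visit, and more under monotone dropout. These sizes rest on assumed correlations and missingness, not on figures in the documents. That no between-arm estimate is specified at 6 weeks, 6 months and 12 months needs no assumption.

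A reader might infer that the trial's main result is at risk. It is not: time to healing is analysed separately, and SAP 2.1 places the health economic assessment outside this plan.

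**What to change.** Replace the analysis-of-variance sentence in SAP 4.6 with a linear mixed model for repeated measures for each score:

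- fixed effects for arm, visit (6 weeks, 6 months, 12 months), arm-by-visit, baseline score and baseline-by-visit;
- an unstructured within-patient covariance;
- every patient with at least one post-baseline form included, with a stated rule for filling in a missing baseline score so that these patients stay in;
- the arm difference and 95% CI reported at each visit, with matching columns added to Table 9.

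Baseline belongs in the model. Without it, precision is lost and change from baseline is not addressed.

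The cost is SAP wording and standard software, with no new data. There is a small downside: the model relies on data being missing at random and on approximate normality, and it does not remove bias if non-return depends on the unseen score. Check residuals and transform skewed scores where needed, as SAP 2.1 already provides.
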